6.7. Health care utilization analysis

For this objective, the analysis will be based on PPS.

Descriptive statistics of the different types of healthcare utilization associated with disease severities will be produced by age interval and by country.

Please note that the heath care utilization reported here are only including medical care that subject were seeking outside the site clinics.

The number and percentage of all episodes(including recurrent) leading to outpatient visit, emergency room visit, Inpatient Admission-Non-Intensive Care, Inpatient Admission-ICU and No physician consultation outside site clinic will be displayed according for WHO RSV LRTI and WHO RSV severe LRTI cases.

The distribution (means and SD) of the number of days the usual care giver or another person took care of the child without missing work, the number of days a person had to stay home specifically because of the illness instead of going at work, and the number of days a person was hired to care for the child specifically because of the illness, will be displayed according to WHO RSV LRTI and WHO RSV severe LRTI status.

For clarity the type of health care utilization for RSV disease episodes is summarised in the table below showing endpoints and analytic methods.

200150 (EPI-RSV-005 BOD)

Statistical Analysis Plan Amendment 1 Final

Subgroup	Case definition	Endpoints	Event considered
By age categories and	WHO RSV LRTIWHO RSV severe	The number and proportion of episodes classified by	All events including
by country	LRTI	Outpatient visit	recurrent
		Emergency Room visit	oronto
		Inpatient Admission (non intensive care)	
		Inpatient Admission (intensive care)	
		No consultation other than site clinic	
		1 Other	
		• By episodes the mean and SD of:	
		The number of days the usual care giver or another person took care of the child without missing work	
		The number of days a person had to stay home specifically because of the illness instead of going at work	
		The number of days a person was hired to care for the child specifically because of the illness	

Table 13Summary of health care utilization for RSV disease episodes for
primary objectives

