9.7.1. Co-primary objectives

• To determine the total health burden of RSV-associated RTI with a suspicion of involvement of the lower respiratory tract.

Incidence rates will be calculated as the number of RSV-associated RTI with a suspicion of involvement of the lower respiratory tract over the number of children-years observations, overall and by subgroups.

Descriptive statistics of the different types of healthcare utilization from all healthcare settings will be provided (proportions, duration, etc.) among RSV-associated RTI with a suspicion of involvement of the lower respiratory tract, overall and by subgroups.

• To assess the performance of the LRTI case definition and severity scale for RSV-associated cases.

Incidences rates will be calculated as the number of RSV-associated LRTI/severe LRTI as classified by the LRTI case definition and severity scale and also as classified by the comparator case definitions (WHO and Nokes, et al [Modjarrad, 2016; Nokes, 2004]), over the number of children-years observations, overall and by subgroups.

Descriptive statistics of the different types of healthcare utilization will be provided (proportions, duration, etc.) among RSV-associated LRTI/severe LRTI as classified by the LRTI case definition and severity scale and also as classified by the comparator case definitions (WHO and Nokes, *et al* [Modjarrad, 2016; Nokes, 2004]), overall and by subgroups.

Statistical analysis of agreement will be performed to compare the different case definitions of RSV-associated LRTI/severe LRTI and key healthcare utilization and health outcomes (the hospitalization status, (P) intensive care unit [ICU] attendance, clinical diagnosis of bronchiolitis or pneumonia, death) overall and by age categories.

Table 15 Comparison of two classifications for severe/Non-severe LRTI

RSV-associated cases		Classification of reference (severe/Non-severe)		
		Hospitalized	Not hospitalized	
Alternative classification (severe / Non-severe)	Severe LRTI (LRTI case definition and severity scale)	True positive (TP)	False positive (FP)	
	Non-severe LRTI (LRTI case definition and severity scale)	False negative (FN)	True Negative (TN)	

2x2 contingency tables such as Table 15 will be provided and the following measures of agreement (with 95% CI) will be calculated:

- Sensitivity: TP/ (TP+FN)
- Specificity: TN/ (TN+FP)
- Positive predictive value (PPV): TP/ (TP+FP)
- Negative predictive value (NPV): TN/ (TN+FN)

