3. OBJECTIVES

3.1. Co-primary objectives

• To determine the total health burden* of RSV-associated RTI with a suspicion of involvement of the lower respiratory tract.

*Health burden refers to burden of the disease imposed on the study population in terms of incidence of the disease and associated healthcare utilization in any healthcare setting.

• To assess the performance of the LRTI case definition and severity scale for RSV associated cases.

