6.6. Incidence analysis

6.6.1. Analysis of co-primary objectives: incidence of RSV respiratory disease

For this objective, the analysis will be based on PPS.

For clarity the analysis of RSV disease incidence is summarised in the table below showing endpoints and analytic methods.

200150 (EPI-RSV-005 BOD)

Statistical Analysis Plan Amendment 1 Final

For each of the following endpoints you could find the case definitions in Table 4:

- RSV RTI with suspicion of involvement of LRT
- WHO RSV LRTI
- WHO RSV LRTI hospitalisation
- WHO RSV severe LRTI
- WHO RSV severe LRTI hospitalisation
- WHO RSV hospitalisation

Table 12Summary of RSV incidence analyses for primary objectives

Endpoints	Incidence analysis method	Subgroup
RSV RTI with suspicion of involvement of LRT WHO RSV LRTI WHO RSV severe LRTI RSV hospitalisation WHO RSV LRTI hospitalisation WHO RSV severe LRTI hospitalisation	Incidence rates of first episode Cumulative probability of first episode (Kaplan Meier)	Overall, by country, by age intervals, by transmission interval
RSV RTI with suspicion of involvement of LRT WHO RSV LRTI WHO RSV severe LRTI RSV hospitalisation WHO RSV LRTI hospitalisation WHO RSV severe LRTI hospitalisation	Proportion affected by all new episodes	Overall and by country, by age intervals
RSV RTI with suspicion of involvement of LRT WHO RSV LRTI WHO RSV severe LRTI RSV hospitalisation WHO RSV LRTI hospitalisation WHO RSV severe LRTI hospitalisation	Incidence proportion of first episode	Overall and by country, by monthly age

For each endpoints listed in the previous table the 95% CI will be computed as described in section 11.1.2 depending on the age category considered and the method listed in the analysis column. Kaplan-Meier curves presenting the cumulative probability of first episode will be displayed overall and by country. The cumulative probability of presenting first episode will be given with its 95% CI at the end of the follow-up.

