12.4. Primary health care utilization analysis

12.4.1. (PO1) To determine the total health burden* of RSV-associated RTI with a suspicion of involvement of the lower respiratory tract

Template 18 Number and percentage of healthcare utilization (supplementary to care provided by study sites) for all episodes of [WHO RSV LRTI, WHO RSV severe LRTI], by age interval [overall, in <each country>] (PPS)

Age interval (Months)	Characteristic	Ν	n	%
0-5	Outpatient visit			
	Emergency room visit			
	Inpatient Admission- Non-Intensive Care			
	Inpatient Admission-with intensive			
	care			
	No consultation other than site clinic			
	Other			
6-11				
0-11				
12-23				
0-23				

N = total number of episodes for the age interval considered

n/% = number / percentage of episodes in a given category with the most intense level of care utilized

Template 19 Frequency of type of caregiver and number of days care utilized per caregiver for episodes of [WHO RSV LRTI, WHO RSV severe LRTI], all episodes considered, by age interval [overall, in <each country>] (PPS)

				Number of days care per caregiver *							
Age interval (Months)	Characteristics	N	n (%)	Mean	SD	Median	Min	Max			
0-5	Usual care giver or another person took care of the child without missing work										
	A person had to stay home specifically because of the illness instead of going at work										
	A person was hired to care for the child specifically because of the illness										
6-11											
0-11											
12-23											
0-23											

N = number of episodes for the age interval considered

n/% = number of episodes for which a caregiver of a given category is provided

SD = Standard deviation

*An event will be taken into account for the calculation of the duration only if type of utilization is reported for that event. The denominator is the n.

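### The healthcare-utilization half of co-primary objective 1 is not tabulated for the population the objective names, and the SAP does not declare the narrowing

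*SAP*

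**What the plan says.** SAP 3.1 gives the first co-primary objective as "To determine the total health burden* of RSV-associated RTI with a suspicion of involvement of the lower respiratory tract". Its footnote makes this a two-part quantity that covers every care setting: "Health burden refers to burden of the disease imposed on the study population in terms of incidence of the disease and associated healthcare utilization". Protocol 2.1.1 says the same.

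Protocol 9.7.1 sets out the matching analysis. Descriptive statistics of utilization "will be provided (proportions, duration, etc.) among RSV-associated RTI with a suspicion of involvement of the lower respiratory tract, overall and by subgroups". Utilization among LRTI and severe LRTI is a separate item there, under the second co-primary objective, so the protocol asks for both.

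SAP 6.7 plans utilization for two groups only. The types of care "will be displayed according for WHO RSV LRTI and WHO RSV severe LRTI cases", and the caregiver-day summaries "will be displayed according to WHO RSV LRTI and WHO RSV severe LRTI status". Table 13, which summarizes utilization for the primary objectives, lists the same two case definitions. SAP 12.4.1 carries the wording of objective 1 as its heading, but the title of Template 18 beneath it begins "Number and percentage of healthcare utilization (supplementary to care provided by study sites) for all episodes of [WHO RSV LRTI, WHO RSV severe LRTI". Template 19 is restricted in the same way.

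**The concern.** The SAP answers the utilization question in a narrower group than the one the objective names. The study's stated purpose (Protocol 3.2.1, SAP 2.2.1) is to find RSV cases of any severity and to measure overall burden, where earlier work was often limited to hospitalized cases. Care used by RSV-positive children with suspected LRT involvement who stay below the WHO thresholds is part of that burden. If it is tabulated nowhere, a reader of the report would take figures from a more severe subset as the utilization result for objective 1.

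**Working it through.** No figure in the plan can be reproduced here, so the check compares passages and then considers direction.

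**1. Is WHO RSV LRTI narrower than the named population?** Under SAP 11.2.1.3 and 11.2.1.5, an RSV-positive child belongs to the named population on attending an examination visit, whatever the final LRTI assessment. A qualifying surveillance report is another route in. WHO LRTI (SAP 11.2.1.4.1) requires cough or difficulty breathing, and also saturation below 95% or a raised respiratory rate, both measured at the examination visit. Every WHO RSV LRTI episode is therefore in the named population, but the reverse does not hold.

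**2. What is planned for each group?**

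| Measure | Named population | WHO RSV LRTI and severe LRTI |
|---|---|---|
| Incidence rate, Kaplan-Meier, proportion affected, incidence proportion | Yes: Table 12 lists "RSV RTI with suspicion of involvement of LRT"; Templates 7, 9, 11, 13 | Yes |
| Inpatient admission | Partly: incidence of RSV hospitalization, with no LRTI criterion (SAP 11.2.1.8) | Yes: Template 18 |
| Outpatient, emergency room, intensive-care split, no consultation | None | Yes: Template 18 |
| Caregiver days | None | Yes: Template 19 |

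**3. Is the change declared?** SAP section 9 declares the replaced outcome categories, the dropped utilization analysis for non-RSV episodes, and a change to how the suspected-LRT endpoint is derived. It does not say that utilization for RSV episodes moved to the WHO groups. Protocol 9.10 requires changes from the planned analysis to be described and justified in the final report.

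**4. Do the data exist?** Swabs are taken at every examination visit, including those without confirmed LRTI (Protocol 6.5.16). Each scheduled examination visit starts a diary card and case eCRF (Protocol Appendix E). Medical attendance is categorized at each examination visit (SAP 11.2.4). RSV status is itself assessed at that visit (SAP 11.2.1.5), so RSV-positive episodes have an examination record.

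**5. Which way do percentages move?** Let f be the share of named-population episodes that meet WHO LRTI, p_L the proportion with a given type of care among those, and p_0 the proportion among the rest. Then

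p_named = f × p_L + (1 − f) × p_0, and the planned figure differs from it by p_L − p_named = (1 − f)(p_L − p_0).

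For inpatient care p_L probably exceeds p_0, so the planned percentage is probably too high for the named population. For outpatient care the sign is unclear, because SAP 11.2.4 keeps only the most intense care per event, and severe episodes may move out of the outpatient category.

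*Illustration only.* Protocol 9.3 expects the RSV LRTI rate to be 8 times the hospitalization rate, which gives p_L = 1/8 = 12.5%. Take p_0 = 0, which gives the widest gap if p_L is at least p_0. The documents do not give f, so a range is assumed:

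| Assumed f | Inpatient share, named population (f × 12.5%) | Episodes absent from Templates 18 and 19 (1 − f) |
|---|---|---|
| 0.3 | 3.75% | 70% |
| 0.5 | 6.25% | 50% |
| 0.7 | 8.75% | 30% |
| 0.9 | 11.25% | 10% |

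**The case against.** The strongest reply is that much of objective 1 is intact. Table 12 gives incidence for the named population by four methods. It also gives incidence for the WHO groups, so utilization in those groups has an incidence figure under the same case definition, although incidence uses first episodes and utilization uses all. RSV hospitalization needs only a positive test and an admission, so admissions below the WHO thresholds are reported. All of this stands, and a reader who inferred that objective 1 as a whole goes unanswered, or that no care at all is reported outside WHO LRTI, would be going beyond the documents.

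A reader might also infer that the burden is understated. That holds for counts of care used, which leave out the episodes below the thresholds. It does not hold in general for Templates 18 and 19, which report percentages and mean days per episode. Restricting these to a more severe subset may raise them.

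Finally, the analyses are descriptive with no hypothesis testing (SAP section 7), no error rate or data collection depends on the point, and the tables could be produced later. That lowers the urgency. It does not remove the mismatch: the protocol specified the table, the SAP leaves it out, and section 9 is silent.

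**Conclusion.** The point holds for the utilization component of co-primary objective 1. Utilization is planned only for WHO RSV LRTI and its severe subset, the protocol specified the wider population, and the change is not declared. For RSV-positive suspected-LRT episodes below the WHO thresholds, outpatient visits, emergency visits, the intensive-care split, no consultation and caregiver days appear in no planned table.

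The effect is incomplete counts, together with per-episode figures that describe a more severe group. The upward shift for inpatient care is probable rather than shown, since it assumes that admission is more common above the thresholds than below. The size cannot be computed because the documents give no ratio of WHO RSV LRTI to the named population. The percentages in the illustration rest on an assumed f, on no admissions below the thresholds, and on a planning ratio that was not stated for the WHO definition.

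**What to change.** Add RSV RTI with suspicion of LRT involvement as a third case definition in SAP Table 13 and in Templates 18 and 19, overall and by country, keeping the two WHO groups beside it. No new data are needed. Each template is repeated overall and for the eight countries in SAP 6.3, so the cost is up to 2 × (1 + 8) = 18 further table versions, with programming that is largely a repeat of what is planned.

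If the sponsor prefers the narrower population, the minimum is to declare and justify it in SAP section 9, carry that into the final study report as Protocol 9.10 requires, and not present Templates 18 and 19 as answering the utilization part of objective 1. This costs a few sentences, but it leaves that part unanswered, so adding the row is the better remedy.

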6.8. Performance of case definitions analysis

6.8.1. Analysis of co-primary objectives: Measures of agreement

For this objective, the analysis will be based on subjects among PPS by RSV case status – Case and Non-case. This analysis will be done considering all new events including recurrent events.

Statistical analysis of agreement will be performed to compare the different case definitions of RSV- LRTI/severe LRTI and RSV hospitalization status – hospitalized and non-hospitalized.

200150 (EPI-RSV-005 BOD)

Statistical Analysis Plan Amendment 1 Final

Three 2x2 contingency tables will be provided and the following measures of agreement (with 95% CI) will be calculated:

Table 14 Comparison of two classifications for RSV LRTI

RSV-associate	d cases	Classificatio	n of reference
		Case	Non Case
Alternative classification (LRTI,	Case	True positive (TP)	False positive (FP)
severe LRTI)	Non case	False negative (FN)	True Negative (TN)

- Sensitivity: TP/ (TP+FN)
- Specificity: TN/ (TN+FP)
- Positive predictive value (PPV): TP/ (TP+FP)
- Negative predictive value (NPV): TN/ (TN+FN)
- Proportion of overall agreement, which is the proportion of cases similarly classified: (TP + TN)/ (TP+FP+FN+TN).
- Cohen's kappa coefficient. The magnitude of the kappa coefficient represents the proportion of agreement greater than that expected by chance.

Such tables will be done for the comparison of each of the 4 LRTI case definitions: WHO, GSK, Nokes, and exploratory (see Table 4) according to the case ascertainment: Case vs Non case, by severity and RSV hospitalization status. Note that GSK, Nokes, and exploratory case definitions (alternative classification) will be compared to WHO case definition (reference classification) but only GSK (reference classification) and Nokes (alternative classification) will be compared to each other.

6.8.2. Analysis of tertiary objectives: case definitions and association with total RSV viral load

Please note that the association of RSV viral load with the incidence of RSV-associated RTI, LRTI and/or severe LRTI (as determined by the LRTI case definition and severity scale) could not be studied since only positive subjects for RSV will have a viral load > LOD.

For this objective, instead a descriptive analysis, based on PPS, will be done considering the 3 age interval:

- 0-11 Months
- 12-23 Months
- 0-23 Months

Two analyses will be realized, on the first episode and on all episodes including recurrent episodes occurring during the age interval considered.

200150 (EPI-RSV-005 BOD)

Statistical Analysis Plan Amendment 1 Final

Descriptive analyses (mean, median, min, max) of the total viral load assessed by the RSV RT-qPCR of first event of RSV RTI, RSV LRTI and severe LRTI cases, with overlapping and non-overlapping disease severity, will be tabulated by age interval for the following endpoints:

- All RSV positive nasal swab samples (see details 6.1.2)
 - RSV asymptomatic
 - RSV RTI
 - WHO RSV LRTI,
 - WHO RSV Severe LRTI
 - RSV asymptomatic (Excluding RSV RTI, WHO RSV LRTI, and WHO RSV severe LRTI)
 - RSV RTI (Excluding WHO RSV LRTI, and WHO RSV severe LRTI)
 - WHO RSV LRTI (excluding WHO severe LRTI)
- Any RSV hospitalisation (see details 11.2.1.8)
 - RSV hospitalization
 - WHO RSV LRTI hospitalization
 - RSV hospitalization (excluding WHO RSV LRTI hospitalization and WHO RSV severe LRTI hospitalization)
 - WHO RSV LRTI hospitalization (excluding WHO RSV severe LRTI hospitalization)
 - WHO RSV severe LRTI hospitalization

The total RSV viral load will be computed by adding the viral load from RSV A tests and the viral load from RSV B tests.

6.9. Neutralizing antibodies over time and protection against RSV disease analysis

6.9.1. Analysis of secondary objective: Association between RSV disease and cord blood neutralizing antibodies

The analysis will be based on PPS and will be done considering the 2 age intervals:

- 0-2 months
- 0-5 months

The analysis will be realized only on the first episode (and not recurrent events) occurring during the considered age interval using a stepwise approach.

Step 1: Descriptive analysis:

Descriptive analyses (seropositivity rate with 95% CIs, geometric mean, median, min, max) of RSV neutralizing antibodies in the baseline cord blood samples will be presented by WHO RSV LRTI and WHO RSV severe LRTI case status; and with overlapping and non-overlapping disease severity.

In addition, descriptive analyses (seropositivity rate with 95% CIs, geometric mean, median, min, max) of RSV neutralizing antibodies in the baseline cord blood samples will be analysed according to the following endpoints:

- All RSV positive nasal swab samples (see details 6.1.2)
 - WHO RSV LRTI
 - WHO RSV LRTI (excluding WHO RSV severe LRTI)
 - WHO RSV severe LRTI
- Descriptive analyses (mean, median, min, max) of the total viral load of RSV according to the quartiles of neutralizing antibodies detected in the cord blood will be described.

Step 2: Cox models:

The impact of the level of RSV neutralizing antibodies in the baseline cord blood samples on the incidence of first event of WHO RSV-LRTI and WHO RSV-severe LRTI separately will be assessed through Cox models.

Univariate and multivariable Cox models will be presented. The following covariates may be considered in the multivariable model

- General:
 - Country of birth
 - Gender
 - Time of birth relative to the transmission season
- Characteristics at birth:
 - Gestational age at birth
 - Birth weight
 - Apgar at 5 mins of age
 - Caesarian section
- Family history:
 - First degree relative with family history of asthma

Statistical Analysis Plan Amendment 1 Final

- Living environment and household composition:
 - Highest education level of the mother
 - Highest education level of the father
 - Number of people living in the household at month 3
 - Number of other children (<18 years old) living in the household at month 3
 - Subject in regular close contact with toddlers at month 3
 - The child live in a surrounding where people smoke daily at month 3
 - Breast feeding *

* Time dependent covariate; status is yes of subject ever breastfed from DOB until the end of breastfeeding given in the surveillance visit. Last day of month will be imputed for any partial date of breastfeeding end date.

Covariates with univariate p-value less than 0.1 will be included in the multivariable model. The number of covariates included in the model will depend on the number of events (at least 10 events per covariates).

Please note that the multivariable model will be performed only if the number of events is sufficient (at least 10 events per covariates). In addition, depending on the data other models could be explored or the model could be simplified.

Step 2-a: RSV neutralizing antibodies classified as a binary variable: Seropositive and seronegative:

In a first step, the RSV neutralizing antibodies in the baseline cord blood samples will be introduced in the model as binary variable. If the effect of RSV neutralizing antibodies as binary variable is significant we process to the next step.

Step 2-b: RSV neutralizing antibodies classified as semi-quantitative variable: Ouartiles

In a second step, the RSV neutralizing antibodies levels will be introduce in the model using quartiles. And the Cox models will be performed as describe in the previous paragraph (RSV neutralizing antibodies as quantitative variable – Step 2-a). If the effect of neutralizing antibodies as semi quantitative variable is significant, we proceed to next step.

Step 2-c: RSV neutralizing antibodies classified as continuous variable:

In a third step, the RSV neutralizing antibodies levels might be treated as continuous variable in Cox models to evaluate how each unit of neutralizing antibody level change impacts on the above clinical outcomes. The Cox models will be performed as describe in the previous section (with log of RSV neutralizing antibodies as quantitative variable). For the subjects with antibody level below the LLOQ, a value of LLOD/2 will be imputed.

Note that depending on the results, a quantitative association between RSV-associated LRTI, RSV-associated severe LRTI and RSV neutralizing antibodies in the baseline cord blood samples could be further explored and described more in details in a separate Additional Analysis Request.

6.9.2. Analysis of secondary objective: prevalence of RSV infection at 2, 4, 6, 12, 18 and 24 months

The analysis will be based on PPS sub-cohort for this objective.

Descriptive analyses (seropositivity rate with 95% CIs, geometric mean, median, min, max) of RSV neutralizing antibodies at 2, 4, 6, 12, 18 and 24 months will be presented.

Prevalence of infection will be determined at the time of the analysis based on the measured antibody titer *vs*. the expected antibody level at the time of sampling based on the individual baseline (cord blood) value and the average, modelled decay rate for subjects with blood sampling at time point 2, 4, 6, and 12 month. RSV infection is defined as titers 2-fold higher than expected value. For subjects with blood sampling during second year of life, a sample with positive result will count as prevalence of infection.

All exact 95% CI will be two-sided, based on the Clopper-Pearson based on a mathematical relationship (see Fleiss et al (2003), p. 25) between the F distribution and the cumulative binomial distribution.

